#### **Assessments of fertility**

Medical documentation of oophorectomy, hysterectomy, or tubal ligation must be retained as source documents. Subsequent hormone level assessment to confirm the woman is not of childbearing potential must also be available as source documentation in the following cases:

1. Surgical bilateral oophorectomy without a hysterectomy
2. Reported 12 months of natural (spontaneous) amenorrhea with an appropriate clinical profile.

In the absence of the above medical documentation, FSH testing is required of any female participant regardless of reported reproductive/menopausal status at screening.

### **8.4.4 Appropriateness of safety measurements**

The safety assessments selected are standard for this indication/participant population.

### **8.4.5 Injection/Infusion site reaction**

Any local tolerability symptoms/signs related to injection will be reported as adverse events and followed until resolution.

## 8.5 Additional assessments

### 8.5.1 Pharmacokinetics

PK samples will be collected at the visits defined in the Assessment Schedule ([Table 8-1](#)). Follow instructions outlined in the laboratory manual regarding sample collection, numbering, processing and shipment. See [Section 8.5.2.1](#) regarding the potential use of residual samples for more information.

If participants cannot visit the site for lab assessments conducted through central labs, local lab collection may be used during a Public Health emergency as declared by Local or Regional authorities, i.e., pandemic, epidemic or natural disaster, that limits or prevents on-site study visits.

Commercially Confidential Information

For standard pharmacokinetic abbreviations and definitions see the list provided at the beginning of this protocol.

The following pharmacokinetic parameters will be determined using the actual recorded sampling times and non-compartmental method(s) with Phoenix WinNonlin (Version 6.4 or higher):  $C_{max}$ ,  $T_{max}$ ,  $AUC_{last}$  from the plasma concentration-time data. Additional parameters may be estimated as relevant.

The linear trapezoidal rule will be used for AUC calculation.

Commercially Confidential Information

Commercially Confidential Information

Commercially Confidential Information

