Study design	
This is a randomized, placebo-controlled, investigator- and participant-blinded study to evaluate the efficacy, safety, tolerability, and pharmacokinetics of HSY244 in participants with AF. An initial cohort (Cohort 1) of approximately 29 participants (approximately 20 participants receiving HSY244) is planned to be enrolled to evaluate a single 150 mg i.v. dose of HSY244 for AF cardioversion to sinus rhythm.
 
Commercially Confidential Information
 
Participants with AF that meet clinical criteria for direct current cardioversion will be screened, and on Day 1, after eligibility is confirmed, administration of a 15 minute i.v. infusion of HSY244 or placebo will occur. Participants will then be monitored for cardioversion to sinus rhythm. For those remaining in AF after 90 minutes, direct current cardioversion can be performed. Participants will be monitored for at least 3 hours, although overnight observation will be available. Participants will be evaluated for safety and pharmacokinetic assessments during end of study assessments, which are to occur on Day 5 (96 hours post dose) ± 24 hours. An interim analysis in Cohort 1 is planned after approximately 10 participants have received HSY244 and completed end of study assessments.
 
Commercially Confidential Information

Study population	
The study population will include hemodynamically stable men and women between 18 and 80 years of age with a clinical indication for direct current cardioversion of AF, with the current AF episode lasting between 6 hours and 60 days.
 
In Cohort 1, a total of approximately 20 participants will receive HSY244 and a total of approximately 29 participants with AF will be randomized. The randomization ratio will be a 5:1 ratio of HSY244 and placebo.
 
Commercially Confidential Information

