**Table 8-1 Assessment Schedule**

Epoch	Screening	Treatment										
Visit Name	Screening 	Day 1								Day 2 	End of Study	Post Study Safety Contact
Visit Numbers 	1	101								102	199	
Days	-3 to 1	1								2	5	Last treatment +30
Time (post-dose)	-	0min	5min	10min	15min ±5 	30min ±5 	60min ±5 	90min ±5 	180min ±5 	24h ±4	96h ±24	-
Informed consent	X											

Commercially Confidential Information

Inclusion / Exclusion criteria	S	S										
Medical history/current medical conditions	X											
Study drug administration		X										
Injection/Infusion site reaction		X	X	X	X	X	X	X	X	X	X	
Demography	X											
Vital Signs	X	X 	X	X	X	X	X	X	X		X	
Body Height	X											
Body Weight	X										X	
Physical Examination	S 	S				S		S	S		S 	

Epoch	Screening	Treatment										
Visit Name	Screening 	Day 1								Day 2 	End of Study	Post Study Safety Contact
Visit Numbers 	1	101								102	199	
Days	-3 to 1	1								2	5	Last treatment +30
Time (post-dose)	-	0min	5min	10min	15min ±5 	30min ±5 	60min ±5 	90min ±5 	180min ±5 	24h ±4	96h ±24	-
Hepatitis screen	S											
HIV screen	S											
Alcohol Test and Drug Screen	S											
Pregnancy and assessments of fertility 	S 										S 	
Hematology	X	X 									X	
Clinical Chemistry	X	X 									X	
Urinalysis	X										X	
PK blood collection		X 			X 	X	X	X	X		X	
Electrocardiogram (ECG)	X	X 				X		X	X		X	
Continuous digital 12-lead Holter		X 										

Commercially Confidential Information

Epoch	Screening	Treatment										Post Study Safety Contact
Visit Name	Screening 	Day 1								Day 2 	End of Study	
Visit Numbers 	1	101								102	199	
Days	-3 to 1	1								2	5	Last treatment +30
Time (post-dose)	-	0min	5min	10min	15min ±5 	30min ±5 	60min ±5 	90min ±5 	180min ±5 	24h ±4	96h ±24	-

Commercially Confidential Information

Adverse Events												X	
Concomitant medications												X	
Concomitant therapies												X	

Commercially Confidential Information

Study completion information													X	
Safety Follow up Call														S

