X Assessment to be recorded in the clinical database or received electronically from a vendor

S Assessment to be recorded in the source documentation only

 Visit structure given for internal programming purpose only

 Allowed screening period is 72 hours; Screening and Day 1 activities are allowed to occur on the same day

 All assessments should be completed prior to direct current cardioversion (if deemed necessary by the Investigator)

 Assessment to be done pre-dose

 Complete physical examination to be done

 All pre-menopausal women who are not surgically sterile will have pregnancy testing

 Sample drawn at end of infusion

 Commercially Confidential Information

 Assessment windows as specified apply only to blood draw assessments

 Can occur on site or via phone call

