**Table 12-1 Non-compartmental pharmacokinetic parameters**

AUC last	The AUC from time zero to the last measurable concentration sampling time (t last ) (mass x time x volume  )
C max	The maximum (peak) observed plasma drug concentration after single dose administration (mass x volume  )
T max	The time to reach maximum (peak) plasma drug concentration after single dose administration (time)

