5.1 Variables

The PK variables of interest are:

- AUClast: the AUC from time zero to the last measurable concentration sampling time (tlast)
- Cmax: The maximum (peak) observed plasma drug concentration after single-dose administration
- Tmax: The time to reach maximum (peak) plasma drug concentration after single dose administration (time)

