5.2 Descriptive analyses

HSY244 plasma concentration data will be listed by treatment, participant, and visit/sampling time point. Descriptive summary statistics will be provided by treatment and visit/sampling time point, including the frequency (n, %) of concentrations below the LLOQ and reported as zero.

Summary statistics will include mean (arithmetic and geometric), SD, CV (arithmetic and geometric), median, minimum, and maximum. An exception to this is Tmax where median, minimum, and maximum will be presented. Concentrations below LLOQ will be treated as zero in summary statistics and for PK parameter calculations. A geometric mean will not be reported if the dataset includes zero values. Pharmacokinetic parameters will be calculated as described in Section 5.1 and will be listed by treatment and participant. Additional parameters may be estimated as relevant. Graphical methods will be employed to show mean and individual concentration-time profiles.

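### If the Day 5 PK sample is measurable, the linear trapezoidal rule spans the last 93 h of AUClast with one straight line, which overestimates it and ties it to the visit date

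*Protocol*

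**What the plan says.** - **Integration rule.** Protocol 8.5.1: "The linear trapezoidal rule will be used for AUC calculation". The visible text has no exception for the declining phase. The same section uses the times at which samples were actually taken. The SAP names no other rule.
- **Sampling.** In Protocol Table 8-1 the row "PK blood collection" is marked pre-dose, at 15, 30, 60, 90 and 180 min, and then only at end of study, 96 h ±24 h. Footnote 7 describes the 15 min draw: "Sample drawn at end of infusion". The Day 2 column has no PK draw.
- **Definition.** Protocol Table 12-1 defines AUClast as "The AUC from time zero to the last measurable concentration sampling time", and SAP 5.1 has the same definition. SAP 5.2 refers back to it ("Pharmacokinetic parameters will be calculated as described in" Section 5.1) and sets values below LLOQ to zero.
- **Role.** AUClast is a secondary endpoint (Protocol Table 2-1, SAP 1.2). SAP 5.3 attaches no model or hypothesis to it.

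**The concern.** After an infusion, plasma concentration falls along a convex curve, and a straight line between two points on such a curve lies above it. Over 30 or 60 minutes the difference is small. Over about four days it is not.

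Two things follow when the end-of-study sample is measurable. Most of the reported AUClast is then the area under one line across an interval with no data. And because actual times are used with a ±24 h window, the length of that line depends on when the participant returned, so AUClast varies with scheduling far more than exposure does.

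If the end-of-study sample is below LLOQ, AUClast stops at the last measurable sample, at most 3 h, and this error does not arise. If measurability differs between participants, the summary mixes AUC to 3 h with AUC to about 96 h, and the linear rule widens the gap between the two.

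**Working it through.** The documents give no AUC figure to reproduce. They also show no half-life or LLOQ, so **all kinetics and LLOQ values below are assumptions**.

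**1. Length of the last segment** (Table 8-1): 96 − 3 = 93 h nominal; 72 − 3 = 69 h and 120 − 3 = 117 h at the ends of the window.

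**2. That segment alone.** Let C3 and CT be the concentrations at 3 h and at the visit time T.
- Linear: (C3 + CT)/2 × (T − 3)
- Log: (C3 − CT) × (T − 3) / ln(C3/CT), which is exact for a single exponential

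With f = CT/C3 the ratio linear/log is (1 + f) ln(1/f) / [2(1 − f)]:

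| Assumed C96/C3 | 0.3 | 0.1 | 0.05 | 0.01 | 0.001 |
|---|---|---|---|---|---|
| Linear / exact | 1.12 | 1.41 | 1.66 | 2.35 | 3.46 |

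The ratio exceeds 1 at every value; only its size depends on the drug.

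**3. One full profile.** Infusion time Ti = 0.25 h; two phases with half-lives 0.25 h (95%) and 16 h (5%); λ = ln 2 / half-life. After the infusion, C(t) is the sum over phases of w/(λTi) × (e^(λTi) − 1) × e^(−λt), where w is the phase weight.
- Cmax (15 min) = 0.735; C3 = 0.0445; C96 = 0.000785, so C96/Cmax = 0.00107
- AUC(0–3 h), linear = 0.499
- Last segment, linear: 93 × (0.0445 + 0.000785)/2 ≈ 2.105
- Linear AUClast: 0.499 + 2.105 = 2.604. Closed-form truth 1.479. Ratio 2.604/1.479 = **1.76**
- Linear-up/log-down AUClast = 1.487. Ratio 1.487/1.479 = **1.01**
- Share of linear AUClast from the last segment: 2.105/2.604 = 81%

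**4. Grids of profiles, visit at 96 h.** Main grid (36): initial half-life 0.15, 0.25, 0.5 h; terminal 8, 12, 16, 20 h; terminal weight 0.02, 0.05, 0.10. Wider grid (100): initial 0.15, 0.25, 0.5, 1 h; terminal 6, 8, 12, 24, 48 h; weight 0.01, 0.02, 0.05, 0.10, 0.20. Ratios are AUClast / true AUC(0–96 h) in profiles with C96 at or above the assumed LLOQ.

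| Grid | Assumed LLOQ | Measurable | Linear / true | Log-down / true |
|---|---|---|---|---|
| Main | Cmax/100 | 0 of 36 | no error | no error |
| Main | Cmax/1000 | 12 of 36 | 1.50–2.02 (median 1.77) | 0.99–1.17 (median 1.00) |
| Main | Cmax/10,000 | 26 of 36 | 1.45–2.39 (median 1.86) | 0.99–1.26 (median 1.01) |
| Wider | Cmax/1000 | 39 of 100 | 1.12–4.18 (median 1.47) | 0.98–2.32 (median 1.01) |

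Log-down is closer to the truth in every measurable profile of both grids. In the 12 main-grid profiles at Cmax/1000, the last segment is 76 to 90% of linear AUClast.

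**5. Visit date** (main grid, LLOQ Cmax/1000, change from a 96 h visit):

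| Visit | Linear | Log-down | True |
|---|---|---|---|
| 72 h (12 profiles) | −21% to −17% | −4.6% to −2.3% | −4.5% to −2.2% |
| 120 h (5 still measurable) | +19% to +21% | +1.7% to +2.3% | +1.7% to +2.0% |

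**6. Mixed measurability** (same 12 profiles). AUClast with a measurable end-of-study sample, divided by AUC(0–3 h), is 4.1 to 10.1 under the linear rule, 2.9 to 6.4 under log-down and 2.6 to 6.4 in truth. The visit date alone can decide measurability: 23, 12 and 5 of the 36 profiles are measurable at 72, 96 and 120 h.

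**The case against.** The strongest objection is that the error may never occur. It needs a measurable Day 5 sample, and on the main grid all 36 profiles escape it at LLOQ = Cmax/100 and 24 of 36 at Cmax/1000. This stands as a condition on the point. It is not a rebuttal, because nothing visible says the sample will be below LLOQ. Protocol Table 4-1 predicts exposure below a physiological threshold at 3 h, but that is not an assay limit and does not tell us C3 relative to Cmax.

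The size also depends on the grid. On the wider grid, some profiles with a 48 h terminal half-life show only 1.12 to 1.26, while at Cmax/100, where the main grid shows no error, 16 of 100 are measurable with ratios of 1.13 to 2.57. No single figure should be read as a prediction for this drug.

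Parts of Protocol 8.5.1 and all of 12.5.2 are blacked out and could hold a partial AUC or further PK detail. They could not hold a different general rule without contradicting the visible sentence.

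Changing the rule does not cure everything. The mixing of 3 h and 96 h intervals comes mainly from the schedule and the definition of AUClast, and most of it remains under log-down. Finally, AUClast is only summarised descriptively, and the visible text ties no decision to it. That limits the consequence but does not make a biased summary preferable to a better one from the same samples.

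**Conclusion.** The point holds, conditionally. If end-of-study samples are measurable, the planned rule overestimates AUClast. The direction is certain for a convex decline. The size is not: about 1.5 to 2-fold on the main assumed grid at LLOQ = Cmax/1000, and 1.1 to 4.2-fold on the wider one. AUClast also shifts by roughly 20% for a one-day change in visit date, where true AUC moves by less than 5% (main grid, same LLOQ). If no end-of-study sample is measurable, there is no error of this kind.

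The change is worth making but does not bear on the trial's main conclusion: it touches one descriptive secondary endpoint. The sponsor holds the half-life and LLOQ and can settle at once whether the condition applies.

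**What to change.** In Protocol 8.5.1, replace the integration sentence with: *AUC will be calculated by the linear-up/log-down trapezoidal rule.*

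Two optional clarifications:
- State in SAP 5.2 that a below-LLOQ value after the last measurable sample is not integrated into AUClast.
- Report AUC(0–3 h) beside AUClast, which gives every participant with a measurable 3 h sample a common interval. Protocol 8.5.1 and SAP 5.2 already allow additional parameters.

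**Cost.** One sentence and no new samples. It needs a written amendment (Protocol 14.1) and can go with the next one. AUClast will come out lower than under the linear rule. Some error from the unsampled 3 to 96 h interval remains: up to 1.17-fold in the 12 main-grid profiles, and up to 2.3-fold on the wider grid, where the linear rule reaches 4.2-fold. Dependence on whether the end-of-study sample is measurable also remains.

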## **9 Study discontinuation and completion**

### **9.1 Discontinuation and completion**

#### **9.1.1 Study treatment discontinuation and study discontinuation**

The Investigator must discontinue study treatment for a given participant if, he/she believes that continuation would negatively impact the participant's well-being.

Study drug administration must be discontinued under the following circumstances:

- Participant withdraws consent
- Development of new complete bundle branch block (QRS duration >120ms) for a participant with a normal QRS duration at baseline as determined by the Investigator's interpretation of the ECG findings or an increase in QRS duration that in the opinion of the Investigator may be a risk to participant safety
- QTcF >500 ms for those individuals with a normal QTcF at baseline as determined by the Investigator's interpretation of the ECG findings, or an increase in QTcF that in the opinion of the Investigator may be a risk to participant safety
- A change in atrioventricular conduction that in the opinion of the Investigator may be a risk to participant safety
- An increase in the resting heart rate to >130 beats per minute sustained for >2 minutes as determined by the Investigator, unless there is an obvious alternative explanation other than administration of study drug
- Hypotension, defined as >20 mmHg systolic blood pressure drop (repeat measurement) that is (a) symptomatic or (b) sustained to the point requiring medical intervention
- Any moderate or higher CNS-related AE that in the opinion of the Investigator is suspected to be related to the study drug
- A seizure
- A severe or serious adverse event
- Hypersensitivity reactions and/or injection site reactions of moderate severity or greater

If discontinuation of study drug administration occurs, the investigator should make a reasonable effort to understand the primary reason for the participant's premature discontinuation of study drug administration and record this information.

Participants who discontinue study drug administration or who decide they do not wish to participate in the study further should NOT be considered withdrawn from the study UNLESS they withdraw their consent (see 'Withdrawal of Informed Consent' [Section 9.2](#)).

**Where possible, they should return for the assessments indicated** in the Assessment Schedule ([Table 8-1](#)). If they fail to return for these assessments for unknown reasons, every effort (e.g., telephone, e-mail, letter) should be made to contact the participant/pre-designated contact as specified in the lost to follow-up section ([Section 9.2.1](#)). This contact should preferably be done according to the study visit schedule.

If the participant cannot or is unwilling to attend any visit(s), the site staff should maintain regular telephone contact with the participant, or with a person pre-designated by the participant. This telephone contact should preferably be done according to the study visit schedule.

After study drug administration discontinuation, at a minimum, in abbreviated visits, the following data should be collected at clinic visits or via telephone/email contact:

- New / concomitant treatments
- Adverse Events / Serious Adverse Events

The Investigator must also contact NIRT to register the participant's discontinuation from study treatment.

If discontinuation occurs because treatment code has been broken, please refer to Emergency breaking of treatment code section ([Section 6.6.3](#)).

### **9.1.2 Replacement policy**

Participants who discontinue study drug administration before completion will be replaced except for those participants who discontinued due to adverse drug reactions or adverse events from study procedures.

## **9.2 Withdrawal of informed consent**

Participants may voluntarily withdraw consent to participate in the study for any reason at any time. Withdrawal of consent occurs only when a participant:

- Does not want to participate in the study anymore

and

- Does not want any further visits or assessments

and

- Does not want any further study related contacts

In this situation, the investigator should make a reasonable effort (e.g., telephone, e-mail, letter) to understand the primary reason for the participant's decision to withdraw their consent and record this information.

Where consent to the use of Personal and Coded Data is not required, the participant therefore cannot withdraw consent. However, they still retain the right to object to the further use of their Personal Data.

Study treatment must be discontinued and no further assessments conducted, and the data that would have been collected at subsequent visits will be considered missing.

Further attempts to contact the participant are not allowed unless safety findings require communicating or follow-up.

All efforts should be made to complete the assessments prior to study discontinuation. If the participant agrees, a final evaluation at the time of the participant's study discontinuation should be made as detailed in the Assessment Schedule (Table 8-1).

Novartis Institutes for BioMedical Research will continue to retain and use all research results (data) that have already been collected for the study evaluation.

### **9.2.1 Lost to follow-up**

For participants whose status is unclear because they fail to appear for study visits without stating an intention to discontinue or withdraw, the investigator must show "due diligence" by documenting in the source documents steps taken to contact the participant, e.g., dates of telephone calls, registered letters, etc. A participant should not be considered as lost to follow-up until due diligence has been completed or until the end of the study.

### **9.2.2 Study stopping rules**

The study will be stopped, and no further dosing will be performed pending a full safety review, if any of the following criteria are met:

- 1 or more study treatment related serious adverse events (SAEs) are reported
- At least 3 participants experience a similar AE which is assessed as either moderate or severe in intensity, and is related to study treatment
- Any moderate adverse event that in the opinion of the investigator is indicative of a nervous system process of major clinical significance (such as stroke, seizure, acute psychosis or delirium) and is related to study drug administration
- 3 or more participants experience symptomatic sinus tachycardia with a resting heart rate >120 bpm that is sustained for >90 minutes during the observation period following study drug administration, unless there is an obvious alternative explanation other than administration of study drug
- The Sponsor considers that the number and/or severity of AEs suggest that there is a significant safety concern.

If one of the above stopping rules is met, the Competent Authorities and IRB/IECs will be informed of the temporary halt of study conduct according to local regulations. In addition, PIs will be informed of the temporary halt and based on the outcome of the safety review, participants will be notified and given appropriate guidance should any safety concern be identified. The study may resume following the safety review, if the Investigator and Sponsor agree it is safe to proceed and after approval to restart the study is obtained from the Competent Authorities and IRB/IECs.

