## **10 Safety monitoring and reporting**

### **10.1 Definition of adverse events and reporting requirements**

#### **10.1.1 Adverse events**

An adverse event (AE) is any untoward medical occurrence (e.g., any unfavorable and unintended sign [including abnormal laboratory findings], symptom or disease) in a clinical investigation participant after providing written informed consent for participation in the study. Therefore, an AE may or may not be temporally or causally associated with the use of a medicinal (investigational) product.

The Investigator has the responsibility for managing the safety of individual participant and identifying adverse events.

Novartis Institutes for BioMedical Research qualified medical personnel will be readily available to advise on trial related medical questions or problems.

The occurrence of adverse events must be sought by non-directive questioning of the participant at each visit during the study. Adverse events also may be detected when they are volunteered by the participant during or between visits or through physical examination findings, laboratory test findings, or other assessments.

Adverse events must be recorded under the signs, symptoms, or diagnosis associated with them, accompanied by the following information (as far as possible) (if the event is serious refer to [Section 10.1.2](#)):

1. The severity grade
  - mild: usually transient in nature and generally not interfering with normal activities
  - moderate: sufficiently discomforting to interfere with normal activities
  - severe: prevents normal activities
2. Its relationship to the study treatment. If the event is due to lack of efficacy or progression of underlying illness (i.e., progression of the study indication) the assessment of causality will usually be 'Not suspected.' The rationale for this guidance is that the symptoms of a lack of efficacy or progression of underlying illness are not caused by the trial drug, they happen in spite of its administration and/or both lack of efficacy and progression of underlying disease can only be evaluated meaningfully by an analysis of cohorts, not on a single participant
3. Its duration (start and end dates or ongoing) and the outcome must be reported
4. Whether it constitutes a SAE (see [Section 10.1.2](#) for definition of SAE) and which seriousness criteria have been met
5. Action taken regarding with study treatment.

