#### **10.1.2 Serious adverse events**

A serious adverse event (SAE) is defined as any adverse event [appearance of (or worsening of any pre-existing)] undesirable sign(s), symptom(s), or medical conditions(s) which meets any one of the following criteria:

- fatal
- life-threatening

Life-threatening in the context of a SAE refers to a reaction in which the participant was at risk of death at the time of the reaction; it does not refer to a reaction that hypothetically might have caused death if it were more severe (please refer to the ICH-E2D Guidelines).

- results in persistent or significant disability/incapacity
- constitutes a congenital anomaly/birth defect
- requires inpatient hospitalization or prolongation of existing hospitalization, unless hospitalization is for:
  - routine treatment or monitoring of the studied indication, not associated with any deterioration in condition of AF
  - elective or pre-planned treatment for a pre-existing condition that is unrelated to the indication under study and has not worsened since signing the informed consent
  - social reasons and respite care in the absence of any deterioration in the participant's general condition
  - treatment on an emergency outpatient basis for an event not fulfilling any of the definitions of a SAE given above and not resulting in hospital admission
- is medically significant, e.g. defined as an event that jeopardizes the participant or may require medical or surgical intervention to prevent one of the outcomes listed above

Medical and scientific judgment should be exercised in deciding whether other situations should be considered serious reactions, such as important medical events that might not be immediately life threatening or result in death or hospitalization but might jeopardize the participant or might require intervention to prevent one of the other outcomes listed above. Such events should be considered as "medically significant." Examples of such events are intensive treatment in an emergency room or at home for allergic bronchospasm, blood dyscrasias, or convulsions that do not result in hospitalization or development of dependency or abuse (please refer to the ICH-E2D Guidelines).

All new malignant neoplasms will be assessed as serious under “medically significant” if other seriousness criteria are not met.

Any suspected transmission via a medicinal product of an infectious agent is also considered a serious adverse reaction.

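### The one-case nervous-system stopping rule names only moderate events, so read literally a related severe, non-serious event does not halt dosing

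*Protocol*

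**What the plan says.** Protocol section 9.2.2 lists five conditions, any one of which stops dosing pending a full safety review:

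1. "1 or more study treatment related serious adverse events (SAEs) are reported".
2. "At least 3 participants experience a similar AE which is assessed as either moderate or severe in intensity", where the event is related to study treatment.
3. "Any moderate adverse event that in the opinion of the investigator is indicative of a nervous system process of major clinical significance", where the event is related to study drug. Stroke, seizure, delirium and acute psychosis are the examples given.
4. Symptomatic, sustained sinus tachycardia in three or more participants.
5. "The Sponsor considers that the number and/or severity of AEs suggest that there is a significant safety concern".

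Section 10.1.1 grades adverse events as mild, moderate or severe, the last defined as "severe: prevents normal activities". Whether the event is an SAE is recorded as a separate item.

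Section 9.1.1 sets the rules for stopping an individual's study drug. They include "Any moderate or higher CNS-related AE that in the opinion of the Investigator is suspected to be related to the study drug" and, as a separate item, "A severe or serious adverse event".

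**The concern.** The third condition is the only one written for a single nervous-system event, and it names one grade. Because severe is a separate grade, a severe event does not meet it as worded. The rule is then stricter for the milder event, and no safety rationale supports that.

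The bullet adds to the SAE rule only for events that are not serious, since a related SAE already halts the study at one case. That is exactly where the wording fails.

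Nervous-system effects are a named risk of this target. Section 4.5.1 cites seizure susceptibility in GIRK2-knockout mice, and euphoria, ataxia and impaired motor skills with another GIRK1/4 inhibitor at high doses. Section 10.1.1.1 makes seizure-related events the adverse events of special interest. Meeting a stopping rule also brings notice to authorities and ethics committees, and their approval before restart, so whether it has been met should not rest on inference.

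**Working it through.** There is no stated figure to reproduce. The check is to follow one event through the rules.

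**Step 1. One related nervous-system event of major clinical significance, not classified as serious, under section 9.2.2.**

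| Condition | Graded moderate | Graded severe |
|---|---|---|
| 1. Related SAE | Not met | Not met |
| 2. Similar event in at least 3 participants | Not met at one case | Not met at one case |
| 3. Single nervous-system event | **Met: study halts** | **Not met on a literal reading** |
| 4. Sinus tachycardia | Not applicable | Not applicable |
| 5. Sponsor judgement | Possible | Possible |

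**Step 2. Can 'moderate' be taken to include 'severe'?** The protocol's own usage points the other way. Condition 2, directly above, names both grades. The individual-level nervous-system rule in section 9.1.1 says moderate or higher. Elsewhere, then, the authors name the higher grades when they mean to include them.

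**Step 3. Does severe imply serious?** No. Section 10.1.1 defines severity by effect on normal activities and records seriousness separately, and section 9.1.1 lists severe and serious as alternatives. The protocol therefore allows for severe events that are not serious.

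**Step 4. Does section 9.1.1 close the gap?** No. It stops one participant's 15-minute infusion, not dosing of later participants, and it has nothing to stop if the event begins after the infusion ends.

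**Step 5. How different are a one-case and a three-case trigger?** Illustration only. Let p be the assumed chance per treated participant of a related, severe, non-serious nervous-system event of major significance. The number treated, n, is 20 (the protocol's approximate figure for HSY244 in Cohort 1), or 24 (29 × 5/6 = 24.2, from the stated total and the 5:1 ratio).

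- P(at least 1) = 1 − (1 − p)^n
- P(at least 3) = 1 − (1 − p)^n − n·p·(1 − p)^(n−1) − [n(n−1)/2]·p²·(1 − p)^(n−2)

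For n = 20 and p = 0.02:

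- P(at least 1) = 1 − 0.6676 = 0.332
- P(at least 3) = 1 − 0.6676 − 0.2725 − 0.0528 = 0.0071

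| Assumed p | n = 20: at least 1 | n = 20: at least 3 | n = 24: at least 1 | n = 24: at least 3 |
|---|---|---|---|---|
| 0.5% | 9.5% | 0.01% | 11.3% | 0.02% |
| 2% | 33.2% | 0.7% | 38.4% | 1.2% |
| 5% | 64.2% | 7.5% | 70.8% | 11.6% |

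The three-case columns treat all such events as similar to each other, which condition 2 requires; if they differ in kind, the three-case trigger is less likely still.

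**The case against.** The strongest reply is that almost nothing falls in the gap. To escape, an event must be severe, drug-related, of major clinical significance and yet not serious. Section 10.1.2 makes an event serious if it jeopardizes the participant or may need intervention to prevent a serious outcome, and its examples of medically significant events include "convulsions that do not result in hospitalization". Most severe related seizures and strokes would be SAEs and halt the study under condition 1. This stands, and it is why the practical effect is small. It does not empty the set: medical significance is a judgement, and a brief, self-limited delirium or psychosis could be graded severe and judged non-serious.

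Second, a sensible reader would take 'moderate' as a floor. That is probably the intent, but the text does not say it and the neighbouring rules do.

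Third, sections 8.4 and 10.1.1.1 require seizure-related events to be reported to the sponsor within 24 hours, the latter whatever their severity or causality, so the sponsor could act quickly under condition 5. This is true for seizure, but that route does not cover delirium or psychosis, and the halt remains discretionary.

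Fourth, the binomial figures hold the other rules silent. A drug that causes severe non-serious events would plausibly also cause moderate or serious ones, each of which halts the study at one case. This also stands. The figures are not the probability that dosing wrongly continues, and they probably overstate the practical gap considerably.

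**Conclusion.** The concern holds. As worded, section 9.2.2 halts the study for one moderate related nervous-system event of major significance but not for one severe event of the same kind, unless that event is serious, is the third similar case, or the sponsor chooses to act. This rests on a literal reading; the likely intent was moderate or higher.

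Practical impact is low, because the seriousness definition captures most of these events. The documents give no event rate, so the probabilities show only how far apart the two triggers are, under assumed rates of 0.5% to 5%. The change should still be made: this is a participant-protection rule for a named risk, and as written it gives a perverse result.

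**What to change.** In the third condition of section 9.2.2, insert 'or severe' after 'moderate' and leave the rest of the sentence, including the examples and the relatedness requirement, unchanged. 'Moderate or higher', as in section 9.1.1, would do equally well.

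The cost is two words in the next protocol amendment. Endpoints, analysis and sample size are unaffected.
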